#### **4.5. SCREEN FAILURE**

All individuals who signed the ICD and withdraw their consent for participation in the study or fail to meet at least one of the eligibility criteria during the initial evaluation will be considered a "screen failure" and their data will not be considered in the final report (except for screen-failed subjects with an AE, in which case the demography, subject disposition, and AE information will be entered in the electronic data capture [EDC] system).

An individual who is screen-failed but may qualify at a later time may be re-screened at the PI's discretion, but the individual should be treated as a new candidate (i.e. new subject ID, new ICD, etc.). Any individual who screen fails and has an AE will not be re-screened.

## 5. SAMPLE SIZE

A sufficient number of subjects will be screened to enroll up to approximately 125 subjects in order to finish with at least 96 subjects (targeting 48 subjects per cell). Enrollment will be evenly distributed across all Fitzpatrick skin types (i.e. an approximately equal number of subjects will be enrolled per skin type per cell, targeting 8 subjects per Fitzpatrick skin type per cell to complete the study).

Refer to section 8.4 for the sample size determination rationale.

If the final overall sample size is smaller than expected (i.e. less than 96 subjects complete the study), a protocol deviation should be recorded and communicated to the Sponsor.

## 6. INVESTIGATIONAL STUDY MATERIALS

The Sponsor has ensured that there is sufficient safety data to support the human use of the investigational study materials (i.e. the IPs and auxiliary products).

### 6.1. IDENTITY OF INVESTIGATIONAL STUDY MATERIALS

The following investigational study materials will be provided under authorization of the Sponsor:

**Table 1. IP and Auxiliary Product List**

Product Identity (as Labeled)	Identification Number	Regulatory Classification and US Marketing Status	Product Type	Included in	
				Active Cell	Sham Cell
AM & PM Cleanser a (plus commercial name: ██████████ ██████████)	██████ ██████████	Cosmetic, Marketed	Auxiliary Cleanser	✓	✓
AM Moisturizer (with SPF 30) (plus commercial name: ██████████ ██████████ ██████████)	██████ ██████████	OTC Monograph Drug, Marketed	Auxiliary Moisturizer	✓	✓
PM Mask Treatment	██████████	Device, Non-Marketed	IP – Active	✓	
PM Mask Treatment	██████████	Device, Non-Marketed	IP – Sham		✓
Mask Activator b	██████████	Device, Non-Marketed	IP – Active	✓	
Mask Activator b	██████████	Device, Non-Marketed	IP – Sham		✓

aA few additional units of the cleanser will be provided to the Site for on-site usage by subjects prior to acclimation, as needed.

bEach PM Mask Treatment is controlled by a corresponding Mask Activator, which turns the mask on/off (Active cell only) and displays how many treatments are still available for use (with each Mask Activator limited to 5 uses). The active and sham Mask Activators are identical except for battery type (the active Mask Activator has more efficient batteries to facilitate the light therapy treatments). The active and sham PM Mask Treatments are structurally identical except the sham wiring has been disabled. Consequently, subjects in the Active cell will receive a fully functional PM Mask Treatment and Mask Activator which will toggle the mask on/off and track the number of remaining treatments available. Subjects in the Sham cell

will receive a functional Mask Activator that will track the number of remaining “treatments” but will not actually activate the sham PM Mask Treatment. A set of Mask Activators will be supplied to subjects at Baseline (Visit 2) and Week 4 (Visit 4). A countdown timer will also be provided to subjects in each cell to audibly define the 10-minute usage period for parity (since the sham mask will not light up).

The IPs will be manufactured by the Sponsor or its agents according to Good Manufacturing Practices; the auxiliary products will be commercially sourced. A Letter of Non-Significant Risk will be provided to the PI for use of the non-marketed devices in this study. OTC Drug Facts will be provided to the PI as reference safety information for the AM Moisturizer, and the ingredient list for each of the auxiliary products is provided in Appendix III.

## 6.2. LABELING

A label will be affixed to each IP unit or packaging and any brand markings on the devices will be over-labeled. The IP labels may contain (but are not limited to) fields for the following information:

- Protocol Number
- Product Identity (see table in section 6.1)
- Randomization Number
- “CAUTION: Investigational Device. Limited by United States law to investigational use.”
- Directions
- Warnings
- Study Site Identification
- Net Contents
- Site Emergency Contact Information
- Storage Information
- Unit #

One IP starter kit (kit 1) and one IP refill kit (kit 2) will be provided for each randomization number. Each starter kit will contain one PM Mask Treatment and seven Mask Activators (each either active or sham, as applicable for the randomization number). Each refill kit will contain fourteen Mask Activators (either active or sham, as applicable for the randomization number). The subject instructions and cell-specific device package insert (see section 6.5) will be packaged with the products in each kit. Replacement kits will be available, as needed (see section 6.6).

A partial label will be affixed to each auxiliary product unit. The auxiliary product labels may contain (but are not limited to) fields for the following information:

- Protocol Number
- Product Identity (see table in section 6.1)
- “For Participant Use Only”
- Directions
- Study Site Identification
- Site Emergency Contact Information
- Unit #

The auxiliary products will be provided individually (i.e. not in kits) for dispensing as needed. Units of the AM & PM Cleanser will also be available for on-site usage prior to acclimation, as needed.

### **6.3. STORAGE AND ACCOUNTABILITY**

The IP and auxiliary products for this study will be secured in a room or cabinet that is only accessible to Study Site authorized personnel and kept at 5-25°C (41-77°F) with relative humidity up to 60%, with temperature and humidity recorded at least daily on business days.

The PI or designee must maintain adequate records documenting the receipt, use, loss, or other disposition of the IPs and auxiliary products on the Product Dispensing and Accountability Log (or equivalent), which must be filed in the SMF.

The log must identify the IPs and auxiliary products and account for their disposition including specific dates and quantities used/dispensed and returned as applicable.

The log must be signed by the Site designee who used/dispensed and retrieved the IPs and auxiliary products and a copy of the log must be provided to the Sponsor.

At the end of the study, all IP and auxiliary product units (used and/or unused) must be returned to the Sponsor: [REDACTED]

### **6.4. PRODUCT QUALITY COMPLAINTS**

A Product Quality Complaint (PQC) is any written, electronic, or oral communication that alleges deficiencies related to the identity, quality, durability, reliability, or safety of a product, including its labeling, delivery system, or packaging integrity. It also includes device malfunctions.

No PQC form should be filed for issues identified during receipt/inventory of a shipment. Instead, these should be reported as indicated on the receipt letter.

Subsequently, any observation/report of a PQC requires immediate notification of the Sponsor. The PI or designee should complete, sign, and securely send a copy of the PQC form to the SM. The PI/site staff is responsible for detecting and reporting PQCs, and for instructing subjects to do the same, whenever applicable. The PI/site staff must also ensure that products presenting PQCs are not used or that they have their use interrupted upon the identification of a PQC.

PQC information must also be included on the Product Dispensing and Accountability Log (or equivalent). The SM can provide assistance and answer questions related to this process. To aid in the initial conversation and understanding of a PQC, the Site staff may be asked to photograph the issue and send the photograph to the SM. The SM will coordinate the replacement or return of the affected products, if necessary.

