This study will be evaluator-blinded, so the PI/evaluators will not know which treatment cell (Active or Sham) each subject is in. Personnel dispensing the IPs or supervising IP use will not participate in the evaluation of subjects in order to minimize potential bias. IPs will be kept separate from the site personnel involved in assessing or evaluating the subjects, and subjects will be instructed not to discuss their assigned IPs with the evaluators or other subjects. Subjects will also be blinded to the extent possible given the nature of the IPs (as described in section 6.1); to this end, the ICD will indicate, "Not all energy is visible to the human eye. You may not see the LEDs light up." Meanwhile, the package insert for the Active cell (Appendix VIII) indicates "Not all energy emitted by the Mask is visible. You will not see all of the LEDs light up;" the package insert for the Sham cell (Appendix IX) indicates "The Mask is not intended

to emit visible light, so you will not see the LEDs light up.” Subjects should not be exposed to the other cell’s IPs or device package inserts.

The randomization schedule will be used by the Sponsor to generate randomization number-specific single disclosure envelopes. In the event that the PI or medically qualified designee believes an un-blinding is necessary and circumstances allow, the PI or designee will contact the SM who will consult with the DPR to determine whether a code break is needed. If there is a medical emergency and the PI or medically qualified designee deems it necessary to urgently know which IP the subject is using for the subject’s proper medical care, then the PI or designee may break the treatment code immediately by opening the provided randomization number-specific disclosure envelope for that subject. The time, date, and reason for the un-blinding should be noted in the subject’s source document and documentation should be provided to the Sponsor. Upon completion of the study, all disclosure envelopes will be returned to the Sponsor.

Blinding should only be broken for serious, unexpected, and related AEs, and only for the subject in question, or when required by local regulatory authorities.

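### Does letting the PI or a designee sign device-malfunction complaints break the evaluator blind?

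*Protocol*

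**What the plan says.** Protocol 6.4 defines a product quality complaint (PQC) and adds: "It also includes device malfunctions". On duties it says: "The PI/site staff is responsible for detecting and reporting PQCs, and for instructing subjects to do the same, whenever applicable". On the form it says: "The PI or designee should complete, sign, and securely send a copy of the PQC form to the SM". Complaint details also go on the accountability log, and 6.3 states: "The PI or designee must maintain adequate records documenting the receipt, use, loss, or other disposition of the IPs and auxiliary products". The same section has that log signed by the site designee who dispensed and retrieved the products.

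Section 3 makes the PI one of three Expert Graders. Section 6.6 states that the PI and other evaluators will not know a subject's cell, and gives three working rules:

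- Staff roles: "Personnel dispensing the IPs or supervising IP use will not participate in the evaluation of subjects in order to minimize potential bias"
- Physical separation: the devices are held away from anyone who grades.
- Conduct of subjects: "subjects will be instructed not to discuss their assigned IPs with the evaluators or other subjects"

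Footnote b to Table 1 in 6.1 says that the activator switches the mask on and off in the Active cell only and that the sham wiring is disabled. Section 6.6 quotes the two package inserts: sham users are told that the LEDs will not light, active users that not all of them will be seen to light.

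**The concern.** A complaint can carry the treatment code in its content. If a subject writes that her mask stopped lighting, dimmed or lit only in part, the device is almost certainly active. Section 6.4 names the PI first for completing and signing that form, does not restrict the designee to people who do not grade, and does not point to 6.6. The rules in 6.6 speak of dispensing, supervising use, physical separation and what subjects say. None of them mentions a written complaint passed from site staff to the PI. Complaints are dealt with as they arise, so one could reach the PI before the Week 12 grading.

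Subjects are blinded only as far as the devices permit, so the trial relies on evaluator blinding. The PI's score is one third of the averaged primary score (Protocol 8.2.1, SAP 6.4.2) and is also analysed on its own. A bias confined to active subjects would not cancel in the active-sham comparison. The two-of-three grader rule in SAP 6.2 concerns superiority to baseline, so it gives that comparison no protection.

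**Working it through.** **Do the sections conflict?**

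| Task | Who does it | Where |
|---|---|---|
| Complete and sign the complaint form | PI or designee | 6.4 |
| Keep the product records | PI or designee | 6.3 |
| Sign the accountability log | Site designee who dispensed and retrieved | 6.3 |
| Inspect devices for compliance at Weeks 1, 4 and 12 | A trained site designee | 7.2.4 |
| Dispense or supervise use | Staff who do not grade | 6.6 |
| Know the cell | Not the PI or other evaluators | 6.6 |

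Every row can be met at once: a designee who does not grade takes the form. No row requires the PI to take it, and the last row is breached if the PI does so and the content reveals the cell.

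**Which complaints reveal the cell?** Loss of light or partial light points strongly to active. A mask that never lit may be a failed active device or a sham whose user overlooked the insert. Breakage and counter faults can occur in either cell. Only part of the complaint traffic is informative.

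**How large could the effect be?** The only design figure available is in Protocol 8.4: 48 per cell, effect 0.7, two-sided 0.05, power 92%. With an assumed SD of 1.0, the standard error is √(2/48) = 0.204, the noncentrality is 0.7/0.204 = 3.43, and a t test with 94 degrees of freedom has 92.4% power. The stated figure reproduces, so SD 1.0 is a fair working value, though the documents give no SD.

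From the documents:

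- 12 × 7 = 84 evenings; 84/5 = 16.8, so 17 activators used per subject.
- Supplied: 7 + 14 = 21 (6.2).

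Assumed, because the documents are silent:

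- p is the chance that an activator produces a light complaint that reaches the PI before Week 12 grading. Failures are independent.
- b is the points by which the PI shifts the score of each revealed active subject.
- There is no true treatment effect, and covariate adjustment is ignored.

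Share of active subjects revealed: f = 1 − (1 − p)^17. Shift in the three-grader difference: f × b/3. The chance of significance favouring active comes from the noncentral t distribution; without leakage it is 2.5%.

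| p | f (of 48) | Shift, b = 0.5 | SD 0.7 | SD 1.0 | SD 1.5 |
|---|---|---|---|---|---|
| 0.5% | 8.2% (3.9) | 0.014 | 3.1% | 2.9% | 2.8% |
| 1% | 15.7% (7.5) | 0.026 | 3.8% | 3.3% | 3.0% |
| 2% | 29.1% (14.0) | 0.048 | 5.2% | 4.2% | 3.6% |

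With b = 0.25 and SD 1.0 the chances are 2.7%, 2.9% and 3.3%. On the PI's scores alone the shift is f × b, three times as large. With b = 0.5 and the same SD of 1.0, the chances there are 3.9%, 5.7% and 10.5%.

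**The case for a change.** The strongest case for a change is that 6.4 names the PI first, and that the designee wording protects the blind only if the PI never takes the task. A form passed across a desk involves no handling of a device and no remark by the subject to a grader, so on a literal reading the three working rules in 6.6 miss it. The sponsor also took a fainter cue seriously: Amendment 1 over-labels the expiration dates because the lot number beside them could reveal the product. A sentence in 6.4 would cost little.

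Most of the facts stand. The route is real, 6.4 lacks the cross-reference, and the PI-only analysis would be more exposed than the average. Three things weaken the case for a required change.

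- The working rules in 6.6 serve a general statement that evaluators will not know the cell, and that statement covers paper as well as devices. The duties in 6.4, such as interrupting use of a faulty mask, also come close to supervising use, which 6.6 already keeps away from graders.
- Light complaints cannot be said to come from the active arm only, since a sham user can report a mask that never lit.
- The package inserts are not readable here, and parts of 7.2.4 and 7.3 are redacted. Instructions on whom to contact about a fault could stand there, so the absence of a rule cannot be shown.

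**Conclusion.** No change to the plan is needed. Read together, 6.3, 6.4, 6.6 and 7.2.4 let a site meet every requirement by giving mask and activator complaints to a person who does not grade, and the blinding statement in 6.6 leads it there. A reference from 6.4 to 6.6 would be tidy, but leaving it out does not alter the design, the analysis or the reading of the result.

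The effect on the primary comparison is small even on unfavourable assumptions. At SD 1.0 and a 0.5-point PI bias, the false-positive chance favouring active is 2.9% to 4.2% against 2.5%; over SDs of 0.7 to 1.5 the range is 2.8% to 5.2%. These figures rest wholly on assumed failure, leakage and bias rates. Each p must combine device failure, reporting by the subject, passage to the PI and timing before Week 12. The calculation also ignores that a subject holds 21 activators and needs 17, so she may use a spare without complaining. The planned per-grader analyses would show whether the PI's active-sham difference departs from those of the other two graders.

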### **6.5. APPLICATION/USE OF THE IP/AUXILIARY PRODUCT**

At Screening (Visit 1), each subject will be provided with the auxiliary cleanser and the auxiliary moisturizer

to use full-face for the duration of the study. Each subject will be instructed to wash her face twice daily (morning and evening) with the AM & PM Cleanser. In the morning after washing, subjects will apply the AM Moisturizer full-face (the AM Moisturizer may be used again in the evening [after completing the mask treatment, as applicable], if desired). The detailed subject instructions for Visit 1 are in Appendix VI.

At Baseline (Visit 2), each subject will be randomly assigned to also use either the active or sham PM Mask Treatment (with respective Mask Activator) at home for the 12-week treatment period of the study. In the evening after washing, subjects will use the PM Mask Treatment (either active or sham) for 10 minutes. The detailed subject instructions for the treatment period are in Appendix VII, and the device package insert is in Appendix VIII and IX for the Active and Sham cells, respectively.

A 12-week regression period will begin at Week 12 (Visit 5); during the regression period, subjects will continue using the auxiliary products as described previously, but there will be no mask usage. The detailed subject instructions for the regression period are in Appendix X.

See section 7.3 regarding compliance metrics.

## 6.6. RANDOMIZATION/IP ALLOCATION AND BLINDING

Subjects who sign the ICD will be sequentially assigned a Subject ID. The Subject ID will begin with the four-digit center ID (1001) followed by a unique four-digit subject identifier assigned in ascending order and beginning with "1001," resulting in an eight-digit Subject ID (e.g. "10011001," "10011002," etc.). Once a Subject ID has been assigned to a subject, it cannot be reassigned to another subject.

Enrollment in the study will be evenly distributed across all Fitzpatrick skin types. Six strata will be created, with one stratum for each of the six Fitzpatrick skin types. A randomization scheme will be performed separately for each stratum. Upon enrollment in the study, subjects will be allocated to one of the six strata based on their Fitzpatrick skin type. Within each stratum, subjects will then be randomly assigned to one of two treatment cells (Active or Sham). An extra stratum will be created to provide replacement kits as needed (e.g. if a subject misplaces or breaks the PM Mask Treatment in the starter kit) so that there will be a total of seven strata in the study. In the event of a replacement, the site should contact the Sponsor's Clinical Supplies department; subjects will be given a new randomization number from this stratum based on their original treatment assignment. Once a randomization number has been assigned to a subject, it cannot be reassigned to another subject. The randomization scheme will be devised by the Sponsor's Quantitative Sciences Department.

The randomization numbers will be incorporated into the IP labeling, as described in section 6.2.

This study will be evaluator-blinded, so the PI/evaluators will not know which treatment cell (Active or Sham) each subject is in. Personnel dispensing the IPs or supervising IP use will not participate in the evaluation of subjects in order to minimize potential bias. IPs will be kept separate from the site personnel involved in assessing or evaluating the subjects, and subjects will be instructed not to discuss their assigned IPs with the evaluators or other subjects. Subjects will also be blinded to the extent possible given the nature of the IPs (as described in section 6.1); to this end, the ICD will indicate, "Not all energy is visible to the human eye. You may not see the LEDs light up." Meanwhile, the package insert for the Active cell (Appendix VIII) indicates "Not all energy emitted by the Mask is visible. You will not see all of the LEDs light up;" the package insert for the Sham cell (Appendix IX) indicates "The Mask is not intended

to emit visible light, so you will not see the LEDs light up.” Subjects should not be exposed to the other cell’s IPs or device package inserts.

The randomization schedule will be used by the Sponsor to generate randomization number-specific single disclosure envelopes. In the event that the PI or medically qualified designee believes an un-blinding is necessary and circumstances allow, the PI or designee will contact the SM who will consult with the DPR to determine whether a code break is needed. If there is a medical emergency and the PI or medically qualified designee deems it necessary to urgently know which IP the subject is using for the subject’s proper medical care, then the PI or designee may break the treatment code immediately by opening the provided randomization number-specific disclosure envelope for that subject. The time, date, and reason for the un-blinding should be noted in the subject’s source document and documentation should be provided to the Sponsor. Upon completion of the study, all disclosure envelopes will be returned to the Sponsor.

Blinding should only be broken for serious, unexpected, and related AEs, and only for the subject in question, or when required by local regulatory authorities.

## **7. INVESTIGATIONAL PLAN**

### **7.1. STUDY DURATION**

The study will consist of 6 visits\* over 24 weeks with visits scheduled at Screening (Visit 1\*\*), Baseline (Week 0; Visit 2), Week 1 (Visit 3), Week 4 (Visit 4), Week 12 (Visit 5), and Week 24 (Visit 6). Baseline to Week 12 (Visit 2 to Visit 5) will comprise a 12-week treatment period, and Week 12 to Week 24 (Visit 5 to Visit 6) will comprise a 12-week regression period.

As necessary, Visit 3 may be adjusted  $\pm$  2 days and Visits 4-6 may be adjusted  $\pm$  3 days. All scheduling windows are versus the Baseline visit (Visit 2 or [if applicable] the final Visit 2 sub-visit, as described below).

\*If required based on Expert Grader availability, Visits 2-6 may each be separated into up to three sub-visits. In such cases, each sub-visit will be identified by the suffix -A, -B, or -C (e.g. Visit 2A, 2B, and 2C); the date and procedures for that sub-visit will be clearly recorded in the source documentation, and all sub-visits for a particular time point should still occur within the prescribed scheduling window. Imaging and the subject questionnaire may be conducted at one sub-visit, while the clinical and subjective evaluations of efficacy and tolerance may occur at (a) separate sub-visit or sub-visits (before or after the imaging visit, as needed). The subject acclimation and interviews for AEs, compliance, and changes in health/medications will be conducted at each sub-visit. If Baseline (Week 0, Visit 2) is split, the sub-visits will occur within 3 days of one another (e.g. if Visit 2A is on a Monday, the final sub-visit will be completed by Thursday), and subjects will be instructed not to begin IP usage until the final sub-visit is complete. If Visit 5 is split, subjects will be instructed to continue the treatment period instructions until the final sub-visit is complete (i.e. IP will be collected and the regression period will begin at the final Visit 5 sub-visit). If Visit 6 is split, subjects will be instructed to continue the regression period instructions until the final sub-visit is complete (i.e. auxiliary products will be collected at the final Visit 6 sub-visit). The Site will use the fewest sub-visits possible.

**\*\*Screening will occur up to 10 days prior to Baseline (or the first Visit 2 sub-visit, as applicable). If Baseline (or Visit 2A) immediately follows Screening (on the same day), the Visit 1 AE collection and Visit 2 (or Visit 2A) interview for compliance may be waived. All Visit 1 procedures must be completed prior to Visit 2 commencing.**

If a subject misses a scheduled visit but notifies the study site, he/she will be allowed to re-schedule the missed visit if it is within the scheduling window as specified above. If it is outside the scheduling window, the SM should be notified to determine if the visit should be rescheduled outside the scheduling window. Study staff will need to assess subject compliance with product usage to ensure the missed/altered visit did not result in a lack of compliance. A lack of compliance will be documented as a deviation and the Sponsor should be notified.

